Assessing Success of MTA and Pre-mixed Bioceramic in Mature Teeth With Irreversible Pulpitis With Full Pulpotomy.

(GCP)

NCT05853185

Monday, August 21, 2023

[name]

STUDY PROTOCOL

Operational Definition

Irreversible Pulpitis

Patients with a history of pain score of greater than 4 on visual analogue scale during clinical assessment with lingering of pain for more than 10 seconds on cold stimulus.

Apical Periodontitis

Patients with positive response to tenderness on palpation/percussion and presence of radiographic rarefaction will be diagnosed as positive for apical periodontitis.

Success

Modified Clinical and Radiographic Criteria¹

- Clinical criteria of success
 - No history of spontaneous pain or discomfort except for the first 2 days after treatment
 - No tenderness to palpation or percussion and the tooth is functional.
 - Normal mobility with less than 1mm and probing pocket depth less than 4 mm.
 - Soft tissues around the tooth are normal with no swelling or sinus tract.
- Radiographic criteria of success
 - No pathosis evident on the radiograph such as root resorption, furcal pathosis or new periapical pathosis

Materials and Methods

Study Design

Randomized Controlled Trial (RCT)

Setting

This study will be carried out on patients visiting outpatient clinic of Department of Operative Dentistry, Institute of Dentistry, Department of Operative Dentistry, LUMHS, Jamshoro/Hyderabad

Duration of Study

9 months after approval of study from CPSP

Sampling Technique

Nonprobability convivence sampling

Sample Size

In this trial, based on the results of a previous studies showing a success of 73.8%² with Mineral Trioxide Aggregate and 98.4%¹ for other bioceramics for full pulpotomy procedures, the proportion in population 1 (P1; Mineral Trioxide Aggregate) and the proportion in population 2 (P2 Endosequence Bioceramic Root Repair Material) were determined to be total of 64 with 32 in each group based on Kelsey on Openepi with power of 80% with confidence level of 95.

Inclusion Criteria

- Patients with diagnosis of irreversible pulpitis without apical periodontitis
- Either gender
- Lower Age 10 Years – Upper Age 40 Years

Exclusion Criteria

- Teeth with signs of resorption
- Roots with open apices (Immature Teeth)
- Calcified or blocked canals
- Iatrogenic perforations
- Root fractures
- Non restorable teeth
- Negative response to cold testing and presence of sinus tract or swelling.
- No pulp exposure after caries excavation
- Bleeding could not be controlled after pulpotomy in 10 minutes.
- Insufficient bleeding after pulp exposure; the pulp is judged necrotic or partially necrotic.

Data Collection

After approval from CPSP and ethical approval from Liaquat University of Medical & Health Sciences. All patients visiting department of operative dentistry institute of dentistry Liaquat university of medical and health sciences, Jamshoro with diagnosis of irreversible pulpitis without apical periodontal pathosis will be recruited. After meeting with inclusion criteria, they will be informed of the details of procedure and their potential consequences and informed consent will be obtained. Demographic data including age, sex, as well as universal tooth number undergoing treatment will be registered. A history of the chief complaint and a clinical examination including visual inspection of the caries status, restorability of the tooth, palpation, percussion, probing pocket depth, mobility using dental mirror and probe and sensibility via cold testing will be performed. A clinical diagnosis consistent with irreversible pulpitis will be established in all cases based on a history of severe spontaneous lingering pain that could be reproduced by cold testing. Preoperative periapical radiographs will be taken using the parallel technique via a film holder. Pre- and intraoperative data including the electric pulp test (EPT, recorded by reading on electric pulp tester) and binary variables including the cold test, pulpal/periapical status will also be registered.

After anesthesia (lidocaine with 1/80,000 epinephrine), complete caries removal, isolation, and pulp exposure, the pulp chamber will be unroofed with a sterile bur, and the pulp from chamber will then be completely removed with a round-end sterile bur on high speed with very low pressure and copious irrigation. After irrigating the chamber with normal saline, a sterile cotton pellet soaked in 5.25% sodium hypochlorite will gently left over the orifices for 10 minutes to achieve hemostasis. After achieving hemostasis, each tooth will randomly be allocated to 1 of 2 parallel arms using a coin toss test performed by a dental assistant who will not be involved in the study. The pulpotomy agent MTA and EndoSequence Bioceramic Root Repair will then be prepared according to the manufacturer's instructions and placed over the orifices with a thickness of approximately 2–3 mm. The cement will then be covered by a layer of light-cured glass ionomer and the remaining cavity will then be restored with

resin-bonded composite. In case of unsuccessful after pulpotomy, teeth will be managed by other pulp therapy techniques.

Data Analysis

Primary outcome for clinical success will be clinical parameters which will be described in binary units, including post-operative pain which will be performed by asking the patient if there is pain either continuous or intermittent, swelling through visual examination, sinus, or fistula through visual examination of the gingiva and tooth mobility by back of mirror to detect mobility in any direction. This assessment will be performed throughout the study at baseline, 6 days, and 6 months. Secondary outcome will be radiographic assessment to detect presence of radiolucency described in binary at baseline, 6 days, and 6 months through periapical radiograph.

All data will be collected and analyzed in SPSS Version 27. Qualitative data will be presented as frequencies and percentages. Quantitative data will be presented as mean and standard deviation. Chi-square test and Fisher's Exact test will be used for comparisons clinical parameters in two groups. Student's t-test will be used to compare between mean age values in the two groups. Friedman's test will be used to study the changes by time within each group. Kaplan-Meier survival curve will be constructed to calculate the mean survival estimates of the two groups. Comparison between survival times will be performed using Log rank test. The significance level will be set at $P \leq 0.05$.

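### Success is judged by absolute limits on mobility and probing depth that no eligibility criterion mirrors, so a tooth can be randomised already failing

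*Combined protocol and SAP*

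**What the plan says.** All references are to the combined protocol and SAP.

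- **Operational Definition, Success.** Among the clinical criteria is "Normal mobility with less than 1mm and probing pocket depth less than 4 mm". Both limits are absolute. The radiographic criteria do ask whether periapical pathosis is new, but the mobility and pocket criteria contain no such comparison with baseline.
- **Inclusion Criteria.** The disease criterion is "Patients with diagnosis of irreversible pulpitis without apical periodontitis". Apical periodontitis is defined separately: "Patients with positive response to tenderness on palpation/percussion and presence of radiographic rarefaction will be diagnosed as positive for apical periodontitis". Pocket depth and mobility play no part in that definition.
- **Exclusion Criteria.** The nearest entries are "Non restorable teeth" and "Negative response to cold testing and presence of sinus tract or swelling". The others concern resorption, open apices, calcified or blocked canals, perforation, root fracture, absence of pulp exposure, and bleeding. None sets a limit on pocket depth, mobility or marginal periodontal disease.
- **Data Collection.** Before treatment, "restorability of the tooth, palpation, percussion, probing pocket depth, mobility using dental mirror and probe and sensibility via cold testing will be performed". No eligibility threshold is attached to probing depth or mobility.
- **Data Analysis.** The primary clinical outcome is described as pain, swelling, sinus or fistula, and mobility in any direction, each binary, at baseline, 6 days and 6 months. Probing depth is not listed. The between-group tests use no baseline periodontal value.

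**The concern.** Entry rules and success rules should fit together: a unit that enters the trial should be able to succeed. Here a tooth can satisfy every entry criterion and already breach the success definition on the day of allocation. The arms differ only in the pulpotomy material, and nothing in the protocol addresses a pre-existing marginal pocket or loosening. If the breach persists, the tooth is scored as a failure in either arm.

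Such failures carry no information about the comparison. They lower success in both arms, shrink the difference and use up power. The design is sensitive to this because it assumes 98.4% success in one arm, which leaves 1.6% for failures from every cause.

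**Working it through.** **1. The plan's own figure.** Inputs from Sample Size: 73.8% (MTA), 98.4% (other bioceramics), 80% power, 95% confidence, 1:1 allocation, Kelsey formula.

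n per arm = (z₀.₉₇₅ + z₀.₈₀)² × p̄(1 − p̄) × 2 / (p₁ − p₂)², with p̄ = (0.738 + 0.984)/2 = 0.861.

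n = (1.96 + 0.84)² × 0.861 × 0.139 × 2 / 0.246² = 31.01 (31.04 with unrounded z values), which rounds up to 32 per arm and 64 in total. The stated sample size reproduces, so it is not in error on its own inputs.

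**2. Does any other provision close the gap?**

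| Provision | Does it limit pockets or mobility? |
|---|---|
| Without apical periodontitis | No. Defined by tenderness plus radiographic rarefaction |
| Recruitment statement: "with diagnosis of irreversible pulpitis without apical periodontal pathosis will be recruited" | No. Refers to apical disease |
| Restorability exclusion | Not defined by periodontal support; examined as a separate item from probing depth and mobility |
| Sinus tract or swelling exclusion | Does not cover a marginal pocket or a loose tooth |
| Pre-treatment examination | Both are examined, with no threshold attached |
| Between-group analysis | No use of baseline periodontal status |

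**3. Which part applies where.** Mobility is a component under both the Success definition (limit 1 mm) and the Data Analysis list (mobility in any direction, with no threshold). Probing depth is a component under the Success definition only.

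**4. Size.** Let q be the share of randomised teeth, equal in expectation in both arms, that already breach a limit and so count as failed under either material. The documents do not give q; every value below is an assumption. The success rates become 0.738(1 − q) and 0.984(1 − q). Power is by exact enumeration of two binomials with 32 per arm, two-sided 5%. The last column is the Kelsey n per arm for 80% power.

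| q | MTA | Bioceramic | Power, uncorrected chi-square | Power, Fisher | Kelsey n per arm |
|---|---|---|---|---|---|
| 0 | 73.8% | 98.4% | 91% | 76% | 32 |
| 1.6% | 72.6% | 96.8% | 85% | 70% | 35 |
| 3% | 71.6% | 95.4% | 79% | 65% | 38 |
| 5% | 70.1% | 93.5% | 72% | 59% | 43 |
| 10% | 66.4% | 88.6% | 58% | 47% | 56 |

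The 1.6% row is the whole failure margin that the plan allows the better arm (100 − 98.4). Among 64 teeth it means about one tooth (64 × 0.016 = 1.0); 3% means about two (64 × 0.03 = 1.9).

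**5. Sensitivity to single teeth.** Take 24/32 v 31/32 successes, close to the planned rates: Fisher p = 0.026, uncorrected chi-square p = 0.012. One extra unrelated failure in the better arm (30/32) gives Fisher p = 0.082. Two (29/32) give chi-square p = 0.098. The probability of such an imbalance depends on q and is not estimated here.

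**The case against.** **Such teeth may be rare.** Entry stops at age 40, and the documents give no prevalence. The success criteria and the 98.4% rate carry the same reference mark. If that rate was obtained under similar criteria, failures from all causes there were 1.6%, so pre-existing periodontal failures were at most 1.6%, and multiplying by (1 − q) may count some of them twice. This stands as a reason to show small q and not to rely on 5% or 10%. It does not prove that q is small, because neither the source nor its entry rules can be seen from the documents.

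**Existing steps may catch them.** An examiner might reject badly compromised teeth as non-restorable, and the outcome assessment, mobility included, is also scheduled at baseline. This stands in part: a pre-existing finding could be separated later, but no rule says that it will be, and restorability is undefined.

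**The pocket example fails under the other outcome description.** Correct. Under the Data Analysis list a deep pocket alone is not a failure.

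**Stronger readings to avoid.** A reader might infer that such teeth *will* be enrolled; the documents support only that they can be. A reader might also infer bias in favour of one material. Allocation is by coin toss after eligibility is settled, so such teeth are expected equally in both arms.

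**Conclusion.** The mismatch is real and follows from the stated rules: the success limits are absolute and nothing at entry corresponds to them. The mobility component is affected under both outcome descriptions. The pocket component is affected only under the Success definition, and the disagreement between the two sections must be resolved in any case.

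The consequence is dilution and lost power, with chance imbalance possible at 32 per arm. Its size is unknown. At q of 1.6% to 3%, chi-square power falls by about 6 to 12 points (91% to 85% or 79%) and Fisher power by about 6 to 11 (76% to 70% or 65%). The larger losses at 5% and 10% are illustrative only. All these figures take the planning rates as free of such failures and assume that a breach present at entry persists to the assessment. The trial remains analysable, but the point should be settled before outcomes are scored because the remedy needs no new examination.

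**What to change.** **Preferred.** Record the pre-treatment probing depth and mobility for each tooth, and count these components as failure only when the breach is new or worse than at baseline. This loses no teeth and adds no entry rule. The cost is that baseline values must be recorded in a form usable for scoring, and that the scoring rule must state what counts as worse.

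**Alternative.** Reconcile the eligibility list with the success definition, so that teeth already breaching it are not entered. The cost is that some screened teeth are lost and the result applies only to periodontally sound teeth.

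**In either case.** Make the Success definition and the Data Analysis outcome list agree on whether probing depth is a component and on how mobility is scored.

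### Could a tooth retreated after a failed pulpotomy be scored as a success at 6 months?

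*Combined protocol and SAP*

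**What the plan says.** The last sentence of Data Collection reads "In case of unsuccessful after pulpotomy, teeth will be managed by other pulp therapy techniques". Nothing further is said about how those teeth are assessed or counted.

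Data Analysis opens with "Primary outcome for clinical success will be clinical parameters which will be described in binary units". The items are pain, swelling, sinus or fistula, and mobility. Pain is an item "which will be performed by asking the patient if there is pain either continuous or intermittent". On timing: "This assessment will be performed throughout the study at baseline, 6 days, and 6 months". Radiolucency is the secondary outcome at the same visits.

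The Success entry under Operational Definition gives clinical and radiographic criteria. The first clinical criterion is "No history of spontaneous pain or discomfort except for the first 2 days after treatment". The others concern tenderness, function, mobility, probing depth, soft tissue and the radiograph.

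For the analysis, chi-square and Fisher's tests compare the clinical parameters ("Exact test will be used for comparisons clinical parameters in two groups"). Friedman's "test will be used to study the changes by time within each group". Kaplan-Meier curves and a log-rank test are also planned, with no event, event date or censoring rule.

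**The concern.** Retreatment changes what the 6-month visit measures. A tooth that fails after day 6, is retreated and settles can show no pain, swelling, sinus tract or mobility when it is next examined. The outcome items are scored visit by visit, and retreated teeth are not excepted. Scored on current signs, such a tooth would count in favour of the material that failed.

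Most failures are expected in the MTA arm, so masking the same share in both arms would pull the comparison towards no difference. The survival analysis adds a second ambiguity: retreatment could be taken as the event, as a censoring point, or ignored. The same tooth could then be a failure in one analysis and a success in another. With few failures expected, a handful of such decisions could affect the conclusion, and decisions made after the data are seen are open to selection.

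**Working it through.** **The plan's own figure.** Inputs from Sample Size: success 0.738 (MTA) and 0.984 (bioceramic), power 80%, confidence 95%, taken as two-sided alpha 0.05. The Kelsey formula with equal arms is n = (1.960 + 0.842)² × 2 × p̄(1 − p̄) / (p₁ − p₂)², where p̄ = (0.738 + 0.984)/2 = 0.861. So n = 7.849 × 2 × 0.1197 / 0.0605 = 31.04, rounded up to 32 per arm and 64 in all. The stated size reproduces, and it takes every failure as a failure.

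**Expected failures.** MTA: 32 × 0.262 = 8.4. Bioceramic: 32 × 0.016 = 0.5.

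**Effect of masking, by assumption only.** Let m be the share of failures recorded as successes because of retreatment, equal in both arms. Apparent failure is 0.262(1 − m) against 0.016(1 − m), so the gap is 24.6(1 − m) points. Power is by full enumeration of the two binomials at 32 per arm. The documents give no value for m.

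| m | Gap (points) | Power, Fisher | Power, uncorrected chi-square |
|---|---|---|---|
| 0 | 24.6 | 76% | 91% |
| 10% | 22.1 | 67% | 88% |
| 25% | 18.5 | 51% | 79% |
| 50% | 12.3 | 19% | 53% |

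Fisher power is already below 80% at m = 0; that shortfall comes from the test and has nothing to do with retreatment. The table uses overall success, whereas Data Analysis compares separate clinical parameters, for which no rates are given. It shows direction and does not measure the loss in the planned tests.

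**Sensitivity in counts.** At a failure rate of 0.016, the likeliest bioceramic count is 0 (0.984³² = 0.60), followed by 1 (32 × 0.016 × 0.984³¹ = 0.31). Two-sided p-values, masking MTA failures only:

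| Failures, MTA v bioceramic | Fisher | Uncorrected chi-square |
|---|---|---|
| 8 v 0 | 0.0048 | 0.0025 |
| 7 v 0 | 0.0108 | 0.0051 |
| 6 v 0 | 0.0242 | 0.0101 |
| 5 v 0 | 0.0528 | 0.0199 |
| 8 v 1 | 0.0265 | 0.0118 |
| 7 v 1 | 0.0534 | 0.0233 |
| 6 v 1 | 0.1042 | 0.0452 |
| 5 v 1 | 0.1961 | 0.0863 |

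From 8 v 0, three masked teeth are needed before Fisher loses significance. From the less likely 8 v 1, one is enough by Fisher and three by uncorrected chi-square.

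**Which teeth are exposed.** A failure first seen at 6 months has not yet been retreated and cannot be masked. A failure seen at 6 days is on record at that visit. What remains is teeth retreated before 6 months and then scored on current signs alone.

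**What the text implies for those teeth.** Three features point the same way.

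- The retreatment sentence applies only to teeth already judged unsuccessful. Recording one later as a success contradicts the label that led to its retreatment.
- Data Analysis ties its primary outcome to clinical success, the term defined under Operational Definition. The two lists of items differ, but the link is visible.
- The first success criterion is a history, so later comfort does not erase spontaneous pain after day 2. The pain item in Data Analysis includes intermittent pain, which a patient can report only over a period.

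**The case for a change.** The strongest case for a change is that intent is not a rule. The history criterion covers pain and discomfort only. A tooth that failed through swelling, a sinus tract, mobility or a radiographic finding is not caught by it, because the other criteria describe the tooth when examined. The definition gives no event date or censoring rule, so two analysts could build different survival curves. Nor does it say which pain or swelling value a retreated tooth contributes to the separate parameter tests or to Friedman's test. A few sentences would settle this without touching patient care or the sample size.

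All of that is accurate as a description of the text, and the omission stands. It does not show that the plan as written leads to a wrong result. For teeth that failed without pain, the label unsuccessful still applies, whatever sign prompted it. For the survival analysis, the ordinary choice in a trial of treatment success is first failure as the event, with the other teeth censored when last seen, and nothing in the documents points to another. The Friedman point is weak: a retreated tooth can still be examined at 6 months and so has a value. Incomplete rows come from missed visits, which is a different matter.

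**Conclusion.** The concern does not call for a change. The plan leaves a rule unwritten; it does not state a rule that is wrong. Its own language makes failure the evident status of a retreated tooth, and first failure the natural Kaplan-Meier event. Analysts would ordinarily fill the gap that way, and then m = 0: the planning rates stay at 73.8% and 98.4%, and the sample size stays at 64.

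The numerical effect of the other reading is unknown. A drop in the gap from 24.6 to 22.1, 18.5 or 12.3 points needs 10, 25 or 50% of failures to be masked, shares that no document supports. It also needs staff to record as a success a tooth they had already called unsuccessful. At the likeliest bioceramic count, three MTA teeth would have to be misrecorded before Fisher's test changed its answer from 8 v 0.

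This conclusion rests on the word unsuccessful being read together with the protocol's definition of success. A trial report that scored retreated teeth on current signs alone would deserve challenge on that point.

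### The 32 per arm and 80% power were calculated for one success proportion per arm, but the analysis text does not say that this proportion is what will be tested

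*Combined protocol and SAP*

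**What the plan says.** **Sample Size** takes its two inputs from previous studies, "showing a success of 73.8%² with Mineral Trioxide Aggregate and 98.4%¹ for other bioceramics for full pulpotomy procedures", and arrives at a "total of 64 with 32 in each group based on Kelsey on Openepi with power of 80"%, at 95% confidence. That is one proportion per arm and one comparison.

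**Operational Definition, Success** gives criteria that must all be met. The clinical ones cover pain, tenderness, function, mobility, probing depth and soft tissues; one item reads "No tenderness to palpation or percussion and the tooth is functional". Radiographic criteria follow under the same Success heading.

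**Data Analysis** opens with "Primary outcome for clinical success will be clinical parameters which will be described in binary units". It then lists signs, introduced as included examples: pain, swelling, sinus or fistula, and mobility. On timing it says "This assessment will be performed throughout the study at baseline, 6 days, and 6 months". The radiograph is placed apart: "Secondary outcome will be radiographic assessment to detect presence of radiolucency described in binary".

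The closing paragraph of Data Analysis gives both chi-square and Fisher's exact test for clinical parameters, Friedman's test for change within each group, and a log-rank test for survival times. The significance level is 0.05.

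**Data Collection** says that after an unsuccessful pulpotomy "teeth will be managed by other pulp therapy techniques". It does not say how such a tooth is scored at 6 months.

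**The concern.** A power statement belongs to a particular variable, visit and test. Here the variable that was sized is success per tooth, and the analysis text does not carry it forward. Five things are left open:

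- whether the primary analysis uses one success variable or several signs;
- whether success is clinical only (Data Analysis makes the radiograph secondary) or clinical and radiographic (Operational Definition);
- which visit is primary;
- which of two tests with quite different power is used;
- what event the log-rank test counts, and how a failed and re-treated tooth is scored.

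Data Analysis can be followed as written and yield only sign-by-sign tests. Unless one sign accounts for every failure, each such test has fewer failures to work with than success does. With no analysis marked as primary, the result to be reported first can be picked once the data are known.

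**Working it through.** **1. Inputs.** From Sample Size: success 73.8% and 98.4%, so failure 26.2% and 1.6%; 32 per arm; power 80%; confidence 95%. From Data Analysis: P ≤ 0.05. Two-sided testing is assumed, because the documents do not state it.

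**2. The plan's own figure.** The mean success proportion is (0.738 + 0.984)/2 = 0.861, and the difference is 0.246. Kelsey's formula gives

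n per arm = (1.960 + 0.842)² × 0.861 × 0.139 × 2 / 0.246² = 31.04,

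rounded up to 32 per arm, 64 in all. The stated size reproduces. A one-sided calculation gives 25, which does not match, so the two-sided assumption fits the plan.

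**3. Exact power for success.** Let q1 and q2 be the failure proportions. Sum Bin(i; 32, q1) × Bin(j; 32, q2) over all pairs of failure counts (i, j) for which the test gives P ≤ 0.05. With 0.262 and 0.016:

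- Fisher: 0.759
- uncorrected chi-square: 0.913

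The choice between the two tests named in the plan therefore moves power from one side of 80% to the other.

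**4. Exact power if a single sign is tested.** The documents give no rates by sign. Assume that one sign carries a share s of the failures in both arms, so the proportions are 0.262s and 0.016s.

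| Share s | Proportion with the sign | Expected count in 32 v 32 | Fisher | Chi-square |
|---|---|---|---|---|
| 100% (success itself) | 26.2% v 1.6% | 8.4 v 0.5 | 76% | 91% |
| 75% | 19.65% v 1.2% | 6.3 v 0.4 | 51% | 79% |
| 50% | 13.1% v 0.8% | 4.2 v 0.3 | 19% | 53% |
| 25% | 6.55% v 0.4% | 2.1 v 0.1 | 1.4% | 14% |

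**5. Re-treated teeth.** Suppose an assumed half of the failed teeth in each arm are re-treated, are free of signs at 6 months and are scored as successes. The failure proportions become 13.1% and 0.8%, which is the 50% row: 19% (Fisher) or 53% (chi-square), even for the success comparison.

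**6. Actual type I error.** With 13.9% failures in both arms (the mean, 1 − 0.861) and 32 per arm, the same enumeration gives 1.8% for Fisher and 5.4% for uncorrected chi-square. Fisher's lower power is the price of its conservatism here.

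**The case against.** The best defence is that the documents can be read as consistent. Data Analysis speaks of clinical success, and Operational Definition has a matching list of clinical criteria. The chi-square and Fisher tests are given for clinical parameters, and 6 months is the last visit. On that reading, clinical success at 6 months is what is tested. This is a fair reading and may be what was meant. The text does not say so, however, and the reading would still leave open the test, the place of the radiograph and the scoring of re-treated teeth.

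Some stronger readings are tempting but not supported:

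- *That 80% power holds only if one success variable is tested.* One success variable is not enough, since Fisher gives 76% at 32 per arm. Nor is it strictly necessary, since a sign that carried every failure would have the same power as success.
- *That success is certain to go untested.* The text is incomplete on this; it does not exclude a success test.
- *That tenderness and probing depth are dropped at follow-up.* The list of signs is open-ended. They are simply not named.
- *That testing several signs lowers power for success.* By itself it does not. Power falls when a sign that carries fewer failures takes the place of success.
- *That the coin toss is part of this fault.* The plan says "each tooth will randomly be allocated to 1 of 2 parallel arms using a coin toss test", which need not give exactly 32 per arm. That is a separate matter of allocation, and this point does not rest on it.

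The shares by sign are assumptions, and the 25% row under Fisher is the extreme of the range shown.

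**Conclusion.** The concern stands as a gap between the sample size and the analysis. The arithmetic in Sample Size is sound for one success comparison, but no analysis is designated as that comparison. The gap matters because the choices left open change power a great deal: 76% or 91% for success depending on the test, and from 79% down to 1.4% for a sign carrying between three quarters and one quarter of the failures.

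These figures assume the planned proportions, exactly 32 teeth per arm, no missing visits, two-sided testing and independent teeth. The last needs stating, because allocation is by tooth and no limit of one tooth per patient is given. The conclusion that the primary analysis is not specified rests on the text alone and needs none of these assumptions.

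**What to change.** Replace the opening of Data Analysis with one definition, for example:

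> *Primary outcome: success per tooth at 6 months (yes/no) = all Operational Definition criteria for [clinical / clinical and radiographic] success met; a tooth judged unsuccessful and managed by other pulp therapy before 6 months counts as a failure; arms compared by one test named in advance, two-sided P ≤ 0.05.*

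The sponsor fills the bracket by reconciling Operational Definition with Data Analysis. If clinical only is chosen, say that 73.8% and 98.4% are assumed to apply to it. The rule for re-treated teeth concerns scoring only, not their management.

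Name the test and restate its power at 32 per arm, assuming independent teeth: uncorrected chi-square 91% (actual error 5.4%) or Fisher 76% (actual error 1.8%). Define the log-rank event as first failure of the same success definition and make that analysis secondary. Label single signs and day-6 results secondary or descriptive.

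**Cost.** The total stays at 64. The change needs protocol wording and one derived variable. Single-sign tests are no longer primary. Success items not named for follow-up, such as tenderness, function and probing depth, must be scored at 6 months. Palpation, percussion and probing are already in the baseline examination, but function is not listed there. If Fisher is named, the stated power is below 80%.

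### No masking of patient, follow-up examiner or film reader is specified, although pain and radiolucency are open to expectation and one tooth can decide the result

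*Combined protocol and SAP*

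**What the plan says.** Under Data Analysis, the primary outcome is a set of binary clinical findings. Pain is obtained by "asking the patient if there is pain either continuous or intermittent". Soft-tissue signs are recorded as "swelling through visual examination, sinus, or fistula through visual examination of the gingiva". Mobility is checked by hand with the back of a mirror. The secondary outcome is radiolucency, scored present or absent on a periapical film. The time points are baseline, 6 days and 6 months.

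The plan does not say who examines the patient, who reads the film, or whether the patient is told the material. Masking, coding of forms or films, and a second reading are not mentioned.

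One role is kept separate. Under Data Collection, teeth are allocated after hemostasis "using a coin toss test performed by a dental assistant who will not be involved in the study". That separates whoever generates the allocation; it does not cover outcome assessment. The cement is prepared and placed after the toss, so the operator knows the material. In both arms it is then covered by glass ionomer and composite.

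**The concern.** A patient or assessor who knows the material, and who expects one to do better, may report or score a doubtful tooth accordingly. The Sample Size section itself expects a large advantage for one arm: it cites studies "showing a success of 73.8%² with Mineral Trioxide Aggregate" and "98.4%¹ for other bioceramics for full pulpotomy procedures". An assessor aware of that expectation could lean the same way when a pain answer is vague or a film is equivocal. A lean the other way could hide a real difference.

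The trial makes one main comparison on few failures, so a small differential error in scoring matters. The analysis cannot remove it afterwards, because it is built into the recorded data.

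**Working it through.** **1. Planned size.** The Sample Size section gives 73.8% and 98.4%, 80% power, 95% confidence (taken as two-sided) and a "total of 64 with 32 in each group". Kelsey's formula uses the mean proportion (0.738 + 0.984)/2 = 0.861 and the difference 0.246:

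n = (1.960 + 0.842)² × 0.861 × 0.139 × 2 / 0.246² = 31.04, rounded up to 32 per arm, 64 in total.

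The stated figure reproduces and is not in dispute.

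**2. Expected failures.** At the planned rates: 32 × 0.262 + 32 × 0.016 = 8.4 + 0.5 = 8.9, so about 9.

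**3. How many teeth decide the result.** The planned rates correspond to about 31 or 32 successes with EndoSequence (32 × 0.984 = 31.5) and 24 with MTA (32 × 0.738 = 23.6). With EndoSequence fixed at 31/32:

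| MTA | Fisher P |
|---|---|
| 24/32 | 0.026 |
| 25/32 | 0.053 |

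One tooth moves the result across the plan's limit of P ≤ 0.05. The uncorrected chi-square test has the same kind of edge two teeth further on. For 31/32 against 26/32, the statistic is 64 × (31×6 − 26×1)² / (57 × 7 × 32 × 32) = 4.01, P = 0.045. For 31/32 against 27/32 it is 64 × (31×5 − 27×1)² / (58 × 6 × 32 × 32) = 2.94, P = 0.086.

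**4. Effect of differential scoring when the materials are equal.** Assumptions: true success 86% in both arms (the rounded mean of the planned rates), 32 per arm, no dropout. The misclassification rates are illustrative; the documents give none. Observed success in each scenario:

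- One in four EndoSequence failures upgraded: 0.86 + 0.14 × 0.25 = 0.895, about 32 × 0.14 × 0.25 = 1.1 teeth.
- Half of EndoSequence failures upgraded: 0.86 + 0.14 × 0.5 = 0.93, about 2.2 teeth.
- One in ten MTA successes downgraded: 0.86 × 0.90 = 0.774, about 32 × 0.86 × 0.10 = 2.8 teeth.

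The rejection probability at P ≤ 0.05 is summed over every possible 32 × 32 result:

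| Assumed scoring error | MTA observed | EndoSequence observed | Fisher | Chi-square (uncorrected) |
|---|---|---|---|---|
| None | 0.86 | 0.86 | 1.8% | 5.4% |
| 1 in 4 EndoSequence failures upgraded | 0.86 | 0.895 | 2.4% | 7.7% |
| Half of EndoSequence failures upgraded | 0.86 | 0.93 | 5.3% | 15.8% |
| 1 in 10 MTA successes downgraded | 0.774 | 0.86 | 8.2% | 14.3% |
| 1 in 4 upgraded and 1 in 10 downgraded | 0.774 | 0.895 | 15.6% | 25.8% |

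**5. Reading the table.** The plan names both tests without saying which governs. At 86% success, 32 × 0.14 = 4.5 failures are expected per arm. That is below the customary minimum of 5 for chi-square, so Fisher is the more natural column. In the combined row, the assumed MTA downgrade contributes most of the rise.

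**The case against.** - **Silence is not a declaration.** A reader might infer that the trial is open-label. The documents do not say so. They leave out who assesses and whether patients are told. This stands: the supportable statement is that no masking is specified.
- **The components are not equally subjective.** The definition of success under Operational Definition sets a mobility limit of 1 mm and a probing depth limit of 4 mm, requires absence of swelling or sinus tract, and exempts pain in the first 2 days. This stands in part. Swelling, sinus tract and mobility leave less room for expectation. The criteria do not protect a pain answer at 6 days or 6 months, or a doubtful radiolucency.
- **The bias is assumed.** A reader might take 15.6% or 25.8% as this trial's false-positive rate. No document supports the size or direction of those errors. By Fisher, the two upgrade-only scenarios give 2.4% and 5.3%, the second being about the nominal level. This stands, and is why each component is shown separately.
- **Masking may be incomplete.** The operator cannot be masked at placement. The patient has local anesthesia, with no sedation mentioned, and may see or hear the allocation. The cements may look different on film; the documents do not say. Staffing is not described, so whether someone other than the operator can examine is unknown. All of this limits what masking achieves, but it is no reason to omit the steps that remain possible.

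**Conclusion.** The concern holds in this form: the plan specifies no masking of the patient, the follow-up examiner or the film reader, while the operator knows the material and the outcomes include asked pain and a yes/no film reading. This is more than a missing detail, because a team following the text would have no step that protects the comparison.

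The firmest measure of its size is that, near the planned result, one tooth separates P = 0.026 from P = 0.053 by Fisher's test. The false-positive rates, 2.4% to 15.6% (Fisher) or 7.7% to 25.8% (chi-square) against 1.8% or 5.4% without bias, show sensitivity only. They rest on equal true success of 86%, no dropout and assumed scoring errors. The documents do not show that bias will occur. The change is worth making because it costs little.

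**What to change.** Amend Data Collection and Data Analysis as follows:

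1. The patient is not told which material is placed, and the coin-toss result and cement preparation are kept out of the patient's sight and hearing.
2. At each follow-up visit the patient's yes/no pain answer is recorded before the examination.
3. Follow-up forms carry a tooth code and not the material.
4. Films are coded, and whoever reads them does so in mixed order without the code list.
5. The code list has a named holder. If that is the assistant who tosses the coin, reword the statement that this person is not involved in the study; otherwise keep the list sealed elsewhere.
6. State who examines and who reads the films, and that the operator is not masked. State also that masking is partial if the operator examines or reads, or if the cements can be told apart on film.

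The cost is a code list, coded forms and one film-reading session. These steps do not require an added assessor, although the documents do not describe staffing, so the sponsor should confirm who will do each. Sample size, visits, treatment and tests are unchanged.
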